10.9. Reporting Serious Adverse Events to the Sponsor

The Investigator (or delegate) must report all Serious Adverse Events and any UADE to the [REDACTED] Safety Contact listed below within 24 hours of awareness.

Information on SAE (including UADE) must be sent by providing the completed, dated and signed paper Serious Adverse Event form. At a later date, the [REDACTED] Safety Contact will report all information to Chiesi Global Pharmacovigilance, the Clinical Project Manager and the Clinical Research Physician.

Name and Title	Telephone no.	E-mail
██████████ Safety ██████████	Toll free numbers provided separately	████████████████████
████████████████████ Global Pharmacovigilance Chiesi Farmaceutici S.p.A., Parma (Italy)	Phone: ██████████ Fax: ██████████	████████████████████ [contact]

- Reporting of SAEs from the investigator site is from the start of the procedure until the subject's study participation ends. After this date, even if no active monitoring of subjects is required, related SAEs occurring to a subject should be reported if the investigator becomes aware of them.
- Up to the closure of the site, SAEs/UADEs reports should be reported to the ██████████ Safety Contact. New related serious adverse events occurring after the site is closed should be reported directly to the Chiesi Safety Contact.

10.10. Reporting Serious Adverse Events/Unanticipated Adverse Device Effects to Regulatory Authorities/ IRB

The Sponsor or designated CRO will report adverse events to the regulatory authorities in compliance with the timelines and standards of reporting according to local regulations (Guidance for industry and Investigators-Safety Reporting Requirements for INDs and BA/BE studies, December 2012) as well as to the Investigators and Central IRB, if applicable, by MedWatch/CIOMS form. The Investigator (or Sponsor/CRO where required) must inform the IRB per Sponsor instruction upon receipt of the SUSAR notification. An IND and/or NDA Safety Report will be submitted to regulatory authorities unblinded. Participating Investigators and IRB will receive a blinded IND Safety Report, unless otherwise specified.

All UADEs which occur with the medical device will be reported by the sponsor or designated CRO to regulatory authorities, as required, as well as to the Investigators and Central IRB, if applicable, as IND Safety Reports.

The Investigator (or Sponsor/ ██████████ where required) must ensure that the IRB receives a copy of the report and that a copy is also filed within their study files.

10.11. General Notes

- In case of death, a comprehensive narrative report of the case should be prepared by the Investigator and provided to the ██████████ Safety Contact together with the Serious Adverse Event form, retaining a copy on site;
- If an autopsy is performed, copy of autopsy report should be actively sought by the Investigator and provided to the ██████████ Safety Contact as soon as available,

retaining a copy on site;

- All source documents provided by the Investigator or site staff to the [REDACTED] Safety Contact must be carefully checked for respect of confidentiality. All personal subject's data must be redacted.
- Any Adverse Drug Reaction (ADR) occurring with any marketed non-investigational medicinal product and/or concomitant medication during the study must be reported by the Investigator to his/her concerned Health Authority according to the applicable laws. The Investigator is also recommended to report all adverse drug reactions to the relevant Marketing Authorization Holders of the involved medicinal products. Additionally, also conditions of use outside the marketing authorization of the medicinal products (i.e. off-label, overdose, misuse, abuse and medication errors) or from occupational exposure, as well as cases of suspected drug interaction and lack of efficacy should be reported.
- If a neonate is transferred to a continuing care site prior to end of the main phase of the trial, the investigator should ensure that the receiving hospital site is aware that the neonate is participating to the present study and communication should be maintained in order to record any adverse event. Moreover, the investigator of the recruiting site will have to provide the continuing care site with written instruction about management and reporting of SERIOUS AE. After discharge home from the continuing care site a copy of the discharge summary letter should be requested in order to cross reference any adverse events and to contribute to BPD assessment.

10.12. Independent Safety Monitoring Board

An Independent Safety Monitoring Board (ISMB) will be established to ensure the safety of study subjects on an on-going basis. The involvement of independent expert advisors will provide an unbiased evaluation of the overall safety in the study, with particular regard to the incidence of major adverse outcomes (i.e. Serious Adverse Events) following study treatment administration.

The ISMB will be composed by independent Clinicians and one independent Biostatistician.

The ISMB will have periodical face-to face or telephone meetings, as appropriate, and a Safety Assessment Report will be issued after each meeting.

An ISMB meeting will be scheduled after the first 15 neonates will have been enrolled. If no safety concerns will be raised, enrollment will continue and will be extended to newborns with GA at birth between 25⁺⁰ weeks up to 28⁺⁶. Before obtaining a favorable opinion from the ISMB, only newborns with GA from 27⁺⁰ to 28⁺⁶ weeks will be enrolled. Further ISMB meetings will be scheduled after the first 60, 105 and 150 subjects, respectively. *Ad-hoc* ISMB meetings can be scheduled, if needed, in case of unexpected safety issues.

The Sponsor (and other study personnel) may be involved in some parts of the ISMB meetings.

All ISMB members will keep as confidential all information and data deriving from the

ISMB activity, without disclosing them to others.

The complete ISMB guidelines including details regarding the members, duties and responsibilities, work and communication processes, frequency of meetings will be established by the ISMB members during the first meeting and reported in a separate charter.

11. DATA MANAGEMENT

An electronic case report form (eCRF) to be filled in by the investigator and/or his/her designee will be used. Access to electronic systems used for data collection will be granted to the study personnel only after appropriate training.

Front-end edit checks will run at the time of data collection and back-end edit checks will be run by the CRO Data Manager to check for discrepancies and to ensure consistency and completeness of the data.

Conditions pre-existing to the start of the procedure, concomitant procedures (even if recorded in a different form) and adverse events will be coded using the MedDRA dictionary while medications will be coded using the WHO Drug dictionary and Anatomical Therapeutic Chemical classification (ATC). The same dictionaries will be used to code mother's medical history, complications during pregnancy and mother's prenatal medications.

After cleaning of the data, a review meeting will be held to determine the occurrence of any protocol violation and to define the subject populations for the analysis.

Once the database of the main phase study has been declared to be complete and accurate, the eCRF forms will be locked and the planned statistical analysis will be performed. Only authorized and well-documented updates to the study data are possible after eCRF forms lock.

The Investigators will receive electronic copies of the subject data for retention at the investigational sites.

The 24-month clinical assessment data will be collected and recorded in a separate visit of the database: once all the data of the 24-month clinical assessment has been declared to be complete and accurate, the complete database will be locked and the planned statistical analysis for this assessment will be performed.

The complete database, including the main phase data, will be newly transferred. Comparing procedures documenting anything hasn't been changed in the main phase study data, will be prepared and archived in the TMF.

12. STATISTICAL METHODS

12.1. Sample Size

No primary efficacy endpoint was defined in this study since the main objective is to describe the overall safety and efficacy profile of administering poractant alfa with two different

procedures: LISA technique or conventional administration with endotracheal tubes and brief invasive ventilation. A total of 150 neonates will be randomized in the study with a ratio 2:1 to LISA arm (i.e. 100) and conventional administration arm (i.e. 50).

12.2. Populations for analysis

The following populations will be considered for the analysis:

- **Intention-to-Treat population (ITT):** all randomized subjects who will receive at least one dose of study medication.
- **Safety population:** all randomized subjects who will take at least one dose of study medication.

The efficacy analyses population will be performed in the ITT population. The Safety population will be used in the analysis of all safety variables.

In case of deviation between as-randomized treatment and treatment actually received, the treatment actually received will be used in the safety analyses (i.e. an as-treated analysis will be performed).

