6.5 Treatment allocation

A balanced block randomization scheme stratified by investigational site and gestational age group (i.e. from 25⁺⁰ to 26⁺⁶ weeks and from 27⁺⁰ to 28⁺⁶ weeks) will be prepared via a computerized system. Once the neonate’s eligibility to take part in the study is confirmed, neonates will be centrally assigned to one of the two treatment arms (LISA/Poractant alfa or ETT/Poractant alfa) through an IRT system (Interactive Response Technology, combination of voice and web response system and also referred as IVRS/IWRS). Enrollment will be staggered: the gestational age will be restricted to 27⁺⁰ to 28⁺⁶ weeks for at least the first 15 randomized neonates. After ISMB evaluation of safety data from the first 15 neonates, provided no safety concerns are raised, the enrolment will be extended to the whole population (25⁺⁰ to 26⁺⁶ weeks and from 27⁺⁰ to 28⁺⁶ weeks).

The IRT will allocate the subject to a certain treatment group using a list-based randomization algorithm and assign the unique screening number of eight digits: the country will be the first three digits (according to ISO 3166 Numeric Country Code), the investigational site number will be the second two digits and the following three digits will be the progressive numbering of the subject within each site (e.g. for the first USA site the screening numbers will be 84001001, 84001002 etc.). The IRT will also generate a confirmation after every IRT transaction is performed.

The Investigator will call the IRT on admission to receive the subject screening number and randomize the subject and obtain the medication (Poractant alfa) kit numbers. Detailed instructions for use of IRT will be provided to the site.

In the LISA group, the relevant catheter provided by the Sponsor (CHF 6440) will be dispensed and used for administration. In the control group, the endotracheal tubes available at the investigational sites for clinical practice will be used for administration.

The LISA catheter (CHF 6440) will be dispensed by the IRT system.

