9. SAFETY ASSESSMENTS

The following variables will be used to describe the safety of the two procedures:

During procedure for surfactant administration

- Number and percentage of neonates with AEs starting during overall procedure for surfactant administration;
- Number and percentage of neonates with AEs starting during overall procedure for surfactant administration judged related to the procedure;
- Number of AEs occurring during overall procedure for surfactant administration requiring either oxygen alone or an increase in FiO₂ without the need for escalation of invasive or non-invasive ventilator support;
- Number of AEs starting during overall procedure for surfactant administration requiring administration of manual (bag and mask) pressure positive ventilation and related duration of ventilation (non- invasive ventilation);
- Number of AEs starting during overall procedures for surfactant administration requiring endotracheal intubation and related duration of intubation (invasive ventilation);
- Number of AEs starting during overall procedures for surfactant administration requiring circulatory support including administration of crystalloids;
- Number of AEs starting during overall procedures for surfactant administration requiring cardiopulmonary resuscitation including administration of cardiac massage or adrenaline.

After first administration

- Number and percentage of neonates with failed 1st attempt to insert the CHF6440/ETT;
- Number of attempts to the first successful insertion;
- Number of device misallocation (esophageal insertion);
- Number of maneuvers discontinued due to neonate's severe destabilization;
- Duration of the whole procedure (starting from the insertion of laryngoscope up to the removal of the catheter or ETT);
- Duration of surfactant administration (min);
- Heart rate (HR) and respiratory rate (RR) (0, 5, 15 and 30 min, 1 hour, 6 and 12 hours after administration);
- Systolic, diastolic, and mean blood pressure (SBP/DBP/ MBP) (15 and 30 min, 1 hour, 6 and 12 hours after administration);
- Premature Infant Pain Profile (PIPP) score [26] (end of surfactant administration).

During the study

- AEs, including incidence of major neonatal complications of prematurity (listed in [APPENDIX III](#)) and adverse drug reactions (ADRs);
- Blood pressure (SBP, DBP, MBP) at 24, 48, 72, 120 hours post-administration;

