10.8. Recording Adverse Events

All AEs occurring during the course of the study must be documented in the Adverse Event page of the eCRF. Moreover, if the Adverse Event is serious, the Serious Adverse Event Form must also be completed.

It is responsibility of the Investigator to collect all adverse events (both serious and non-serious).

The recording period for Adverse Events is the period starting from the beginning of the procedure until the subject’s study participation ends.

Given the significant amount of possible comorbidities in the study population, any condition diagnosed before the start of the procedure will be considered a baseline condition and will be recorded in the Medical History page of the eCRF. The occurrence or worsening of these conditions during and after the study procedure must be recorded as an AE in the eCRF.

The only exception to this rule is represented by congenital anomalies including major organ malformations, genetic diseases and/or chromosomal abnormalities, that should be reported as baseline conditions even if diagnosed after treatment.

If a clinically significant abnormal laboratory finding or other abnormal assessment detected during the study period meets the definition of an AE and is not assessed as pre-existing, then the AE eCRF page must be completed, as appropriate. A diagnosis, if known, or clinical signs and symptoms if diagnosis is unknown, rather than the clinically significant abnormal laboratory finding, should be reported on the AE eCRF page. If no diagnosis is known and clinical signs and symptoms are not present, then the abnormal finding should be recorded as adverse event.

Occurrence of COVID-19 infection during the study will be reported in the Adverse Events section of the eCRF if symptoms judged related to the infection are present. Every effort should be made by the site to confirm all suspected incidences of COVID-19 in accordance with local diagnostic guidelines. Tests for detecting SARS-CoV-2 infection, as well as their results, will be reported in the eCRF. Documentation of testing and results obtained outside the clinical site, should be collected within 14 days of confirmed diagnosis (or whenever possible) and recorded in the eCRF. For all confirmed cases of COVID-19/SARS-CoV-2 the investigator must follow the standard of care in accordance with local treatment guidelines. All concomitant treatments must be recorded in the eCRF as well.

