For pharmacovigilance purposes, all SAEs should be followed-up in order to elucidate as completely and practically as possible their nature and/or causality until resolution of all queries, clinical recovery is complete, laboratory results have returned to normal, stable condition is reached or until the subject is lost to follow-up. Follow-up may therefore continue after the subject has left the study. In this case, the follow-up will continue with no timelines for related SAEs, while for unrelated SAEs the type and extent of follow-up undertaken will be determined for each individual case and will depend upon the nature (e.g. events with poor prognosis or which do not resolve), severity and medical significance of the event.

AEs related to the procedure for surfactant administration

The procedure for surfactant administration will last from the application of the laryngoscope up to the removal of the CHF 6440 catheter in the LISA treatment group or the ETT in the comparator arm within one hour after the instillation of poractant alfa.

All AEs during procedures for surfactant administration will be carefully monitored and recorded in both arms. Specific focus will have to be paid on the following AEs:

- Obstruction of the CHF 6440 catheter or ETT;
- Bradycardia;
- Neonatal oxygen desaturation;

- Apnoea;
- Hypotension requiring treatment;
- Any episodes of cough, sneezing, choking, laryngospasm, surfactant reflux, vomiting.

A complete qualitative risk assessment has been conducted to identify and mitigate potential safety risks associated with use of CHF 6440 medical device. The results provide evidence that the benefits of using the device outweigh the residual risks and do not highlight any specific additional risk or safety issue than the ones listed above.

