12.3.5. Safety variables

Adverse Events and Neonatal Morbidities

- Number and percent of neonates reporting AEs started during procedure for surfactant administration as well as AEs started during the procedure and judged related to the procedure will be summarized by treatment group.

For LISA group, any AE assessed as related to CHF 6440 catheter will be considered procedure-related.

These events will be also summarized by treatment group based on action required, if any (i.e. supplementary oxygen or transient increase in FiO₂, manual positive pressure ventilation, endotracheal intubation, administration of, crystalloids, or cardiopulmonary resuscitation or administration of adrenaline). The duration of endotracheal intubation and positive pressure ventilation will be

summarized as well.

A subgroup analysis of AEs during procedure for surfactant administration will be performed based on the use of sedation and/or analgesia (Yes/No).

- Incidence of AEs including neonatal complications of prematurity (see [APPENDIX III](#) for complete list), related AEs (ADRs), serious AEs (SAEs) and AEs leading to death will be summarized by treatment group both in term of frequency of neonates with at least one AE and in term of frequency of AEs (number of events). All the aforementioned categories of AEs will be summarized by System organ Class (SOC) and Preferred Term (PT).
- Frequency of neonates with major neonatal morbidities at discharge or 40 weeks PMA (whichever comes first) will be summarized by treatment group.

Vital Sign

- Vital signs parameters (SBP, DBP MBP, HR and RR) will be summarized as absolute and the change from baseline (pre-procedure) by treatment group using descriptive statistics.

Pain assessment

- PIPP score will be summarized by treatment group by means of descriptive statistics.

First administration

- Number of 1st failed attempt to insert the catheter/ETT will be summarized by treatment group. Percentage of neonates with 1st failed attempt will be compared between group using the Cochran-Mantel-Haenszel adjusted for gestational age group. The CMH adjusted difference with its 95% CI will be presented.
- Number of attempts to the first successful insertion will be summarized by treatment group by means of descriptive statistics.
- Number of device misallocation (i.e., esophageal intubation) will be summarized by treatment group by means of descriptive statistics.

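### Section 12.2 leaves neonates whose procedure was started but who got no surfactant out of every safety table, and its as-treated rule means the CMH safety comparisons may not compare the groups as randomised

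*Protocol*

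**What the plan says.** Protocol section 12.2 defines the Safety population as "all randomized subjects who will take at least one dose of study medication" and adds: "The Safety population will be used in the analysis of all safety variables". The ITT population carries the same dose requirement, so no defined set keeps a randomised neonate who was not dosed. Where allocation and actual treatment differ, "the treatment actually received will be used in the safety analyses (i.e. an as-treated analysis will be performed".

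Section 6.5 makes the delivery route the randomised contrast: "neonates will be centrally assigned to one of the two treatment arms (LISA/Poractant alfa or ETT/Poractant alfa". Section 2.1 makes the safety of that route the main objective. Section 10.8 dates the exposure from the laryngoscope: "The procedure for surfactant administration will last from the application of the laryngoscope up to the removal of the CHF 6440 catheter" (or of the tube in the comparator arm). Of adverse events it says: "The recording period for Adverse Events is the period starting from the beginning of the procedure". In section 6.2.3.3 the LISA syringe is connected only once the catheter position has been confirmed, and up to three attempts are allowed.

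The safety variables in section 9 include failed first attempt, oesophageal placement, adverse events starting during the procedure, and one that begins: "Number of maneuvers discontinued due to" (severe destabilisation). Section 12.3.5 plans CMH tests adjusted for gestational age group: "Percentage of neonates with 1st failed attempt will be compared", and likewise BPD, death/BPD, mortality and oxygen use at Day 28.

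**The concern.** A dosed-only, as-treated safety set suits a drug trial, where exposure starts with the dose and a switch is usually an allocation error. Here exposure starts before the dose, and a switch can be a consequence of the randomised procedure failing. This has two results.

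1. A neonate in either arm who was laryngoscoped but received no surfactant by any route is absent from the very tables meant to count failed and abandoned procedures.
2. Several between-group tests, including those on BPD, death/BPD and mortality, are classed as safety and so fall under the as-treated rule. If neonates change device, these tests lose the protection of randomisation. No as-randomised version is planned.

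At stake is the main safety comparison of the study. No confirmatory test is involved.

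**Working it through.** **Step 1: the text.** Section 12.1 gives 100 LISA and 50 conventional neonates (100 + 50 = 150, ratio 2:1) with no power calculation, so there is no design figure to reproduce. The order of events in sections 6.2.3.3 and 10.8 is laryngoscope, attempt or attempts, confirmed position, dose. A first attempt has failed or succeeded, and a manoeuvre may have been discontinued, before any dose. Section 12.2 tests for a dose. Nothing elsewhere in the protocol brings undosed neonates back into a safety analysis.

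**Step 2: how many.** The documents give no failure, non-dosing or switching rate, so these inputs are assumptions:

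- first-attempt failure p = 0.20 or 0.30, equal in both arms;
- three independent attempts (the limit of three is from section 6.2.3.3).

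All three fail in 100 × p³ LISA neonates: 100 × 0.008 = 0.8, or 100 × 0.027 = 2.7. To the nearest whole neonate, k = 1 goes with p = 0.20 and k = 3 with p = 0.30.

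**Step 3: effect on failed first attempt.** Suppose the k neonates leave the LISA row, either because they are undosed and dropped from LISA only, or because they are dosed by tube and enter the ETT row with the tube attempt as the one that counts. In both cases the LISA rate is (100p − k)/(100 − k) and the expected ETT rate stays at p.

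| p | k | LISA rate | ETT rate | LISA − ETT |
|---|---|---|---|---|
| 0.20 | 1 | 19/99 = 19.2% | 20.0% | −0.8 points |
| 0.30 | 3 | 27/97 = 27.8% | 30.0% | −2.2 points |

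The true difference is zero. In 100,000 simulated trials with two gestational age strata (LISA 40/60, ETT 20/30, an assumed split), the CMH test falsely favoured LISA (z < −1.96) in 3.7-3.9% of runs for the first row and 5.1% for the second, against 2.7-2.8% as randomised.

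**Step 4: equal losses.** If each first failure ends undosed with probability p² in both arms, the mean loss is 0.8 LISA and 0.4 ETT neonates (p = 0.20) or 2.7 and 1.35 (p = 0.30). Both rates become (p − p³)/(1 − p³), the difference is 0.0 points, and the false-favour rate is 2.7%.

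**Step 5: precision.** The 95% half-width is 1.96 × √[p(1 − p)(1/100 + 1/50)], which is 13.6 points at p = 0.20 and 15.6 points at p = 0.30.

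**Step 6: discontinued manoeuvres.** If 3 of 100 LISA procedures are discontinued and 1, 2 or 3 of those neonates get no surfactant by any route, the table shows 2/99, 1/98 or 0/97 instead of 3/100. These counts are illustrative.

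**Step 7: death/BPD.** Assume 40% in both arms and k = 1 to 3 LISA neonates with own risk r moved to ETT. The difference is (40 − kr)/(100 − k) − (20 + kr)/(50 + k). For r = 0.2 it is +0.6 to +1.8 points, for r = 0.4 it is 0, and for r = 0.8 it is −1.2 to −3.5 points. The sign depends on r, which is unknown.

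**The case against.** The strongest reply is directed at the as-treated rule. Section 12.2 invokes it only where allocation and treatment differ, which also covers plain allocation errors. It does not define treatment received for a neonate exposed to both devices, and section 6.2.3.3 does not say that tube dosing follows failed catheterisation. A neonate with LISA attempts could be classed as having received LISA, and the data review meeting (section 11) or the SAP may settle this. As-treated display also has a proper use: causality to CHF 6440 is assessed in LISA neonates (section 10.4), and device-related events count as procedure-related in that group (section 12.3.5). This stands. It limits the as-randomised requirement to the CMH comparisons. It does not rescue the dosed-only set, because no SAP can restore an undosed neonate without departing from section 12.2.

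Three stronger readings are tempting, and the documents support none of them.

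- A reader might infer that every failed or discontinued procedure is lost. A neonate given surfactant by any route stays in. Section 6.2.3.5 concerns events while surfactant is being given, when some may already be in, and whether a partial volume counts as a dose is not stated.
- A reader might infer a large built-in advantage for LISA. If the failed catheter attempt were carried into the ETT row, the rates at p = 0.30 and k = 5 would be 25/95 = 26.3% and 20/55 = 36.4%, a gap of 10 points. The protocol does not say that the attempt is carried over, and k = 5 exceeds what three independent attempts give.
- A reader might infer that these events go unseen. Serious events are still reported (section 10.9) and the safety board still reviews them (section 10.12).

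**Conclusion.** The point holds and should be fixed. Section 12.2 itself excludes neonates whose procedure was started but who were not dosed from all safety tables. It also allows the CMH comparisons of failed first attempt, BPD, death/BPD, mortality and Day 28 oxygen use to depart from the randomised groups if device switches occur.

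The size cannot be derived from the documents. Under the stated assumptions the shift in failed first attempt is about 0.8-2.2 points towards LISA, small beside a half-width of about 14-16 points, and zero if undosed losses are equal in both arms. Even then the undosed failures are missing from the counts. For BPD, death/BPD and mortality not even the direction is known. The study calls itself explorative (section 1.1), and section 12.2 confines the as-treated rule to safety, so the efficacy analyses are not under it. That the ITT set is in fact a modified ITT is only a matter of label.

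**What to change.** 1. In section 12.2, define the Safety set as all randomised neonates in whom the procedure was started (laryngoscope inserted), dosed or not.
2. Run the CMH comparisons of section 12.3.5 by randomised group. Keep as-treated summaries for device- and procedure-related adverse events, and as supportive tables elsewhere.
3. State in section 12.2 how a neonate exposed to both devices, or not dosed, is classified in as-treated tables, and that failed first attempt refers to the first device attempted.
4. Optionally, relabel the ITT set as modified ITT.

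The cost is wording in section 12.2 and one extra set of tables. No extra neonates or assessments are needed, and no clinical rule changes.
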